#### 11.2.7 Route of Administration

F-FES is a sterile, intravenously (IV) injectable solution in a volume of  $\leq$  10 mL containing of 0.15 M phosphate buffered saline: < 15% ethanol (v:v). Prior studies have shown that this volume of injectate infused over 2 minutes is well tolerated and minimizes local saturation of SHBG which could limit systemic delivery of F-FES.

#### 11.2.8 Incompatibilities

N/A

#### 11.2.9 Availability

cGMP-grade  $^{18}\text{F}$ -FES will be manufactured on-site in the UW-Madison Radiopharmaceutical Production Facility. This facility has been qualified and approved for production by NCI Cancer Imaging Program (CIP) and ECOG-ACRIN for other FES clinical trials. The investigational pharmacist or qualified nuclear medicine technologist will be the responsible party designated by the investigator.

#### 11.2.10 Side Effects

See Section 8.4 for side effects. The radiation absorbed effective dose equivalent to the whole body from intravenously injected  $^{18}\text{F}$ -FES is estimated to be 0.022 mSv/MBq (488 mrem for a 6 mCi injection). The critical organ is the liver, with an average absorbed dose of 0.13 mGy/MBq. The organ and total body doses associated with  $^{18}\text{F}$ -FES PET imaging are comparable to or lower than those associated with other widely used clinical nuclear medicine procedures and are well below the maximum suggested individual study and annual total body dose of 30 and 50 mGy, respectively, suggested for investigational radiopharmaceuticals by the FDA.

#### 11.2.11 Nursing/Patient Implications

Standard safety precautions required when handling radioactive materials (predominantly during the injection and uptake period) should be followed.  $^{18}\text{F}$ -FES requirements are similar to those used for other PET tracers, such as  $^{18}\text{F}$ -FDG.

### 11.3 Cerianna (fluoroestradiol F-18)

If scheduling conflicts do not permit use of locally produced  $^{18}\text{F}$ -FES, then commercially available  $^{18}\text{F}$ -FES (CERIANNA) will be obtained which is FDA approved for patients with recurrent or metastatic ER+ breast cancer and is being used in a manner that is consistent with its approval.

The use of this product in research is consistent with the criteria for IND exemption in accordance with 21 CFR 312.2(b)(1). Cerianna is a lawfully marketed drug, and this research is not intended to support a new indication or new product labeling.

## 12. STATISTICAL CONSIDERATIONS

### 12.1 Primary Objective

*To compare quantitative  $^{18}\text{F}$ -FES uptake of biopsy-proven DCIS measured using PET/MRI with ER protein levels determined by immunohistochemistry.*

The primary objective is to compare  $^{18}\text{F}$ -FES  $\text{SUV}_{\max}$  from PET/MRI with the ER immunohistochemistry semi-quantitative score obtained by using the Allred score. We will test the hypothesis that  $^{18}\text{F}$ -FES  $\text{SUV}_{\max}$  from PET/MRI correlates well against the ER IHC Allred score. The correlation of the two measures will be evaluated using Spearman correlation. The null hypothesis is  $H_0: p_0=0.00$  and the alternative hypothesis is  $H_1: p_1=0.73$ .

A sample size of 12 patients achieves 82% power ( $\beta=0.20$ ) for detecting an expected correlation coefficient ( $r=0.73$ ) to be significantly different from zero with two-tailed  $\alpha$  value of 0.05 (<http://www.sample-size.net/correlation-sample-size/>). We anticipate enrolling 1 subject every 1-2 months. The number of subjects with ER-negative DCIS will be limited to  $\leq 3$ .

Other measures of  $^{18}\text{F}$ -FES uptake including  $\text{SUV}_{\text{peak}}$ ,  $\text{SUV}_{\text{mean}}$ , tumor-to-normal tissue uptake ratio, and total lesion uptake will also be correlated with the ER immunohistochemistry semi-quantitative score obtained by using the Allred score.

## 12.2 Secondary Objectives

1. To determine the optimal cut-point  $^{18}\text{F}$ -FES uptake value for distinguishing between ER+ and ER-negative DCIS.

Receiver operating characteristic (ROC) curve analysis will be performed to determine the optimal cut-point for  $^{18}\text{F}$ -FES uptake to distinguish ER+ from ER-negative DCIS, as defined by the clinical pathology report. The area under the curve (AUC) for the ROCs and their respective two-sided 95% confidence intervals will be calculated using logistic regression. The optimal cut-off point will be determined by considering the  $^{18}\text{F}$ -FES uptake value with the maximum sensitivity and specificity.

2. To determine the test-retest reproducibility of quantitative assessment of tumor  $^{18}\text{F}$ -FES uptake.

The reproducibility of the two measurements (test-retest) of  $^{18}\text{F}$ -FES uptake in the subjects (up to 5) who elect to undergo a second imaging session will be assessed by intra-class correlation coefficient (ICC) and its 95% confidence interval (47). Additionally, the coefficient of repeatability (CR) and the Bland-Altman plot will be used (48).

3. To determine the optimal cut-point  $^{18}\text{F}$ -FES uptake value for distinguishing between low-risk DCIS and intermediate/high-risk DCIS.

ROC curve analysis will be performed to determine the optimal cut-point for  $^{18}\text{F}$ -FES  $\text{SUV}_{\text{max}}$  to distinguish low-risk DCIS and intermediate/high-risk DCIS. Risk categories will be determined using the Van Nuys Prognostic Index, the Memorial Sloan-Kettering Cancer Center Nomogram, and the research-based Oncotype DX DCIS score. Sensitivity and specificity will be determined with two-sided 95% confidence intervals. The AUCs for the ROCs and their respective two-sided 95% confidence intervals will be calculated using logistic regression.

The optimal cut-off point will be determined by considering the  $^{18}\text{F}$ -FES uptake value with the maximum sensitivity and specificity.

This analysis will be done separately for each risk assessment model.

4. To estimate the association of quantitative  $^{18}\text{F}$ -FES uptake (continuous  $\text{SUV}_{\text{max}}$ ) with research-based Oncotype DX DCIS scores (0-100).

Scatter plots of continuous quantitative  $^{18}\text{F}$ -FES uptake ( $\text{SUV}_{\text{max}}$ ) on the y-axis and research-based Oncotype DX DCIS scores (unitless) on the x-axis will be created to explore the distribution of the measurements. Pearson's or Spearman's rank correlation will be used to evaluate the association between quantitative  $^{18}\text{F}$ -FES uptake and research-based Oncotype DX DCIS score. The correlation coefficient (rho) and 95% confidence interval will be reported.

5. To determine the upgrade rate to invasive cancer at surgical excision.

This percentage will be calculated by dividing the number of patients with invasive breast cancer diagnosed at the time of surgical excision by the number of patients with percutaneous biopsy-proven DCIS in the study.

6. To correlate tumor  $^{18}\text{F}$ -FES uptake with serum estradiol and sex hormone binding globulin levels.

A correlation analysis of serum estradiol and sex hormone binding globulin levels will be performed using Pearson's or Spearman's rank correlation. Scatter plots, correlation coefficients (rho) and 95% confidence intervals will be reported.

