An important molecular target in premalignant and malignant breast tissue is ER, which drives hormone-dependent breast tumor growth, and can be inhibited by endocrine therapy. As shown in invasive breast cancer, ER appears to be an important prognostic factor and predictive biomarker for clinical benefit of adjuvant tamoxifen treatment for DCIS (16). In normal breast tissue, ER is expressed in a minority of cells at low to moderate staining intensity. However, very high levels of ER expression in nearly all cells are noted in most premalignant and noninvasive breast lesions (e.g. hyperplasias, atypia, lobular carcinoma in situ, and non-comedo DCIS) (31). The majority of DCIS express ER protein (approximately 69%; range 49-97%) (32). The exception is high grade comedo DCIS which can have low or no ER expression. Semi-quantitative ER levels measured by immunohistochemistry in DCIS are inversely related to the histologic grade of DCIS and are increased compared to invasive breast cancer (33). Interestingly, tumors cells at sites of focally disrupted myoepithelial cell layers are predominately (86.4%) ER-negative (34).

Expression of ER can be measured in patients through the use of a radiolabeled estrogen ligand, 16 $\alpha$ -F-fluoro-17 $\beta$ -estradiol (F-FES), and positron emission tomography (PET)

imaging (35, 36). Tumoral  $^{18}\text{F}$ -FES uptake, as measured by  $\text{SUV}_{\text{max}}$  with whole body PET/CT imaging, correlates well ( $r=0.56\text{--}0.96$ ) with ER expression in invasive breast cancer, as measured by radioligand binding in fresh tissue and immunohistochemistry in fixed tissue (37, 38). Overall sensitivity of  $^{18}\text{F}$ -FES PET for detection of ER+ breast cancer was 84% (95% CI: 73–91) in four published studies involving 114 patients (35, 37–40). Overall specificity was high at 98% (95% CI: 90–100) demonstrated by absence of  $^{18}\text{F}$ -FES uptake ( $\text{SUV}_{\text{max}}$  less than 1.0) in 51 of 52 histologically benign lesions and ER-negative breast cancer in three studies (35, 38–40).

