## 5. RESEARCH DESIGN AND METHODS

### 5.1 Study Design

This prospective, single-arm, observational, single-institutional research study will enroll women with DCIS scheduled for diagnostic breast MRI for preoperative staging/extent of disease evaluation. The proposed work-flow is described in the schema above. Eligible patients will be consented for participation in the research study which will involve the simultaneous acquisition of F-FES PET imaging data during a standard dynamic contrast enhanced clinical breast MRI performed prior to surgical excision. Patients with ER+ DCIS will be offered to participate in an optional sub-study which will involve a second (test-retest) F-FES PET/MRI examination until we have accrued up to 5 patients. The results of the F-FES PET imaging component of the examination will not be used to guide patient management. However, the clinical breast MRI component of the examination will be interpreted and reported with management recommendation as per routine clinical care. Surgical management, radiation therapy, and adjuvant therapy will follow standard of care. A research-based Oncotype DX DCIS score will be obtained from the surgical specimen for research purposes only since this test is currently not frequently used clinically at our institution (only about 1-5% DCIS patients locally).

Patients with DCIS may also participate in this study if a clinical breast MRI has already been performed. In this scenario, a research F-FES breast PET/MRI will be performed on a separate day as the clinical breast MRI exam prior to surgery.

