#### 5.5.6 $^{18}\text{F}$ -FES PET/MRI Image Analysis

Images will be reviewed for general quality. The known biopsy-proven breast cancer(s) will be identified on the MRI/PET examination based on its known location from the prior clinical breast MRI, if performed, or the patient's previous imaging, as is typically done in routine clinical practice. MRI images will be used to localize the lesion(s), measure the lesion size (in three dimensions), and assign the region of interest (ROI) for PET imaging analysis.

Quantitative analysis of  $^{18}\text{F}$ -FES uptake will be performed at the lesion-level. Standardized uptake values (SUV) will be measured by manually drawing a region of interest (ROI) to encompass the entire lesion guided by the lesion extent visualized on MRI. For the primary objective, the maximum SUV value (SUVmax) will be determined. For potential exploratory analyses, additional uptake values may include SUVpeak (small fixed-size ROI centered on most intense part of tumor), SUVmean (average value), SUVmin (minimum value), SUVsd (standard deviation), tumor-to-normal tissue uptake ratios, FTV (functional tumor volume; i.e. the volume of tumor tissue with increased  $^{18}\text{F}$ -FES uptake) and TLU (total lesion uptake; i.e. the product of FTV  $\times$  SUVmean). A research workstation/software (e.g. Mirada Medical) will be used to perform these advanced quantitative techniques.

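### Section 12.2 takes the 95% CI for the AUC from logistic regression and names no interval formula; with at most 3 ER-negative subjects of 12, complete separation is a realistic result under which the usual intervals collapse to 1.00-1.00

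*Combined protocol and SAP*

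**What the plan says.** Section 12.2, objective 1, plans an ROC analysis of FES uptake for ER+ versus ER-negative DCIS. For the AUC, it says that "their respective two-sided 95% confidence intervals will be calculated using logistic regression". Objective 3 (low-risk versus intermediate/high-risk DCIS) uses the same words. Neither objective names a variance or interval formula, or says what is done when the groups separate completely.

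Section 12.1 plans 12 patients and adds: "The number of subjects with ER-negative DCIS will be limited to" at most 3. It sets no minimum, so 0, 1 or 2 are possible.

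In both objectives the cut-point is the "uptake value with the maximum sensitivity and specificity". Objective 3 adds: "Sensitivity and specificity will be determined with two-sided 95% confidence intervals". Objective 1 has no matching sentence.

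**The concern.** With one predictor, a logistic model ranks subjects exactly as the uptake value does. It therefore adds nothing to the AUC estimate, and its own fit breaks down when the two groups do not overlap. With only three, two or one ER-negative subjects, non-overlap can easily arise by chance and becomes likely if the tracer works well.

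At stake is the precision statement for objective 1. In a separated sample the analyst would have either no interval or one that claims certainty from three subjects, and any replacement would be chosen after seeing the data. The cut-point has a related weakness. Under separation every value in the gap scores 100%/100%, so the cut is not unique, and objective 1 plans no interval to show how little three subjects say about specificity.

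**Working it through.** **The plan's own figure.** The documents give no precision figure for the AUC. The only related number is the 82% power behind n = 12 (Section 12.1; r = 0.73, two-sided 0.05). Fisher's z of 0.73 is 0.929; the bias term 0.73/(2×11) = 0.033 brings it to 0.962. Then 0.962×√9 − 1.96 = 0.926, which gives 82%. So n = 12 reproduces, but it was set for the correlation, not for the ROC analysis.

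**What happens under separation.**
- *Logistic fit.* The likelihood keeps rising as the slope grows, so there is no finite maximum. On a separated 3 v 9 data set one algorithm stopped with a singular matrix; another returned a slope of 141 with a standard error of about 110,000.
- *DeLong.* Every pairwise comparison is won, both variance components are 0, and the interval is 1.00-1.00. With one ER-negative subject that group's component divides by 1 − 1 = 0, so the variance is undefined whether or not the groups separate.
- *Hanley-McNeil Wald.* The variance carries the factor A(1 − A), which is 0 at A = 1.
- *Bootstrap.* Every resample that contains both groups has AUC 1.
- *Penalised fit.* It stabilises the slope but leaves the ranks, and so the AUC of 1 and its zero standard error, unchanged.

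**How often.** Assumptions: equal-variance binormal uptake, one value per subject, m ER-negative and n ER+, d = √2·Φ⁻¹(AUC). Then

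P(separation) = ∫ m·φ(x)·Φ(x)^(m−1)·[1 − Φ(x − d)]^n dx.

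| True AUC (assumed) | 3 v 9 | 2 v 10 | 1 v 11 |
|---|---|---|---|
| 0.70 | 4% | 9% | 23% |
| 0.80 | 11% | 18% | 37% |
| 0.90 | 30% | 40% | 58% |
| 0.95 | 51% | 60% | 74% |

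**Which column applies.** The Introduction puts ER+ DCIS at about 69% (range 49-97%). If 12 subjects enrol at 69% ER+, the cap of 3 is reached with probability 77%, and no ER-negative subject is seen with probability 0.69^12 = 1.2%. At 97% ER+ the latter is 0.97^12 = 69%.

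**An interval that does not collapse.** The Newcombe score-type limits are the values A that solve |Â − A| = 1.96·√V(A), with the Hanley-McNeil variance evaluated at the limit:

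V(A) = A(1 − A)·[1 + (N* − 1)(1 − A)/(2 − A) + (N* − 1)A/(1 + A)]/(mn), N* = (m + n)/2 = 6.

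For 3 v 9 with Â = 1, try A = 0.621. A(1 − A) = 0.2354; the bracket is 1 + 1.374 + 1.916 = 4.290; V = 0.2354×4.290/27 = 0.0374. Then 1.96×√0.0374 = 0.379 = 1 − 0.621, so the lower limit is 0.62. The same equation gives 0.55 for 2 v 10 and 0.40 for 1 v 11. Simulated coverage at AUC 0.70 to 0.984 is 95-96% for 3 v 9 and about 93-97% over all three splits.

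**The cut-point.** If all 3 ER-negative subjects fall on the right side of the cut, the Clopper-Pearson lower limit for specificity is 0.025^(1/3) = 0.292, so the interval is 29-100%. For 9 of 9 ER+ it is 0.025^(1/9) = 0.664, so 66-100%.

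**The case against.** The plan names no interval formula, so it cannot be said that its interval always fails under separation. This stands. An unusual route, such as carrying a profile-likelihood limit for the slope over to the AUC, could give a lower limit below 1. The documents do not describe one, so the supported claim is that the method is under-specified and the usual choices collapse.

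The frequency is also unknown, and this stands too. It depends on an assumed AUC and model. A reader might take the Introduction's 84% sensitivity and 98% specificity, which imply an AUC of 0.984 in this model, and conclude that about 77% of trials would separate at 3 v 9. Those figures come from other settings: the specificity rests on absent uptake "in 51 of 52 histologically benign lesions and ER-negative breast cancer in three studies", and the protocol knows of no FES study in DCIS.

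Three further inferences go too far.
- Adding the chance of no ER-negative subject to the chance of separation gives much larger totals. With no ER-negative subject, no AUC exists under any method; that follows from the missing minimum, not from the interval.
- DeLong coverage at 3 v 9 is only about 84% at AUC 0.70, but separation accounts for 4% of samples there. Most of that loss is small-sample error in a method the plan does not name.
- Objective 1 is not silent on sensitivity and specificity, because choosing the cut requires them. Only their reporting and intervals are unstated.

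Finally, the AUC interval is supporting output of a secondary objective in a feasibility study. The "PET imaging component of the examination will not be used to guide patient management", and no decision rule uses the interval. This limits the weight of the point but does not remove it, since naming a sound interval in advance costs almost nothing.

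**Conclusion.** The point holds. Objectives 1 and 3 need a named AUC interval that survives an estimate of 1. For objective 1 with 3 v 9, the chance of needing it runs from about 4% (AUC 0.70) to 51% (AUC 0.95), and it is higher with fewer ER-negative subjects. The collapse of the usual intervals is mathematical; its frequency rests on the binormal model, the assumed AUC and one value per subject. Section 5.5.6 says that quantitative analysis of "uptake will be performed at the lesion-level", so these numbers would not apply directly if several lesions per patient were analysed. For objective 3 the group sizes are not given, so no frequency is claimed.

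The AUC estimate stays computable in separated samples, and the stated method can be run in most samples that overlap. The primary Spearman test is unaffected. This is a change worth making, not a threat to the trial's main result.

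**What to change.** In Section 12.2, objectives 1 and 3, replace the logistic-regression interval with the rank-based AUC and a Newcombe score-type two-sided 95% CI (Hanley-McNeil variance evaluated at the limit).

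In objective 1 also:
- report sensitivity and specificity at the chosen cut with Clopper-Pearson 95% CIs, in line with objective 3;
- report the full range of tied cut-points;
- label the cut-point hypothesis-generating;
- state that the ROC analysis is not done if there is no ER-negative subject.

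The cost is a few sentences and a few lines of code, with no change to enrolment, sample size or the primary analysis. The downside is a wider, less favourable interval: 0.62-1.00 in place of 1.00-1.00 with three ER-negative subjects, and a nearly uninformative 0.40-1.00 with one. The Clopper-Pearson intervals do not allow for choosing the cut on the same subjects, which is why the label is needed.

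### The SUV cut-points in section 12.2 are chosen and scored on the same 12 or fewer patients, so their sensitivity and specificity will be overstated unless corrected

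*Combined protocol and SAP*

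**What the plan says.** Section 12.2 plans an ROC analysis for ER status (objective 1) and for low versus intermediate/high recurrence risk (objective 3). Under both, the cut-off is the "uptake value with the maximum sensitivity and specificity". No explicit criterion, such as the Youden index, is named.

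For objective 3 the section adds: "Sensitivity and specificity will be determined with two-sided 95% confidence intervals". It also says: "This analysis will be done separately for each risk assessment model". There are three models (Van Nuys, the Memorial Sloan-Kettering nomogram and the research Oncotype score), so there are three searches. Objective 1 promises the AUC with its interval and a cut-point; it does not say in words that sensitivity and specificity will be reported.

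Section 12.1 sets the sample at 12 patients and restricts one group: "The number of subjects with ER-negative DCIS will be limited to" three or fewer. Section 5.7 limits the Oncotype assay to patients with enough remaining tissue, so that analysis may have fewer than 12. Neither section 12 nor any other section provides a validation set, cross-validation or other allowance for the search. The cut-points are listed as secondary objectives, while a separate exploratory objective covers only tumor cell density.

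The Introduction cites a fixed value for absent uptake, SUVmax "less than 1.0) in 51 of 52 histologically benign lesions and ER-negative breast cancer in three studies". Section 12 does not evaluate it.

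**The concern.** A cut-point picked because it makes sensitivity and specificity as large as possible in one sample follows that sample's chance pattern. Its accuracy in the same sample is therefore biased upward, and the bias grows as the groups shrink. Here one group for objective 1 has at most three patients, and objective 3 repeats the search three times.

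At stake are the named cut-points and the point estimates printed beside them. A reader would take these as the performance to expect in the next patients. The plan neither warns of the bias nor supplies a figure with it removed.

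**Working it through.** **The plan's own figure.** The only sample-size statement concerns the primary correlation: "A sample size of 12 patients achieves 82% power" for r = 0.73 against zero, two-sided alpha 0.05.
- Plain Fisher z: Φ(atanh(0.73)·√(12−3) − 1.96) = Φ(0.929·3 − 1.96) = Φ(0.83) = 79.6%.
- With the bias term r/(2(n−1)) = 0.73/22 = 0.033: Φ(0.962·3 − 1.96) = Φ(0.93) = 82.3%.

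The stated 82% is therefore reproduced by a standard variant. No size, power or precision is given for the cut-point objectives.

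**Inputs for the check.**
- From section 12.1: 12 patients, at most 3 ER-negative, hence 9/3 at the cap.
- Assumed: SUV is normal in each group with equal variance; the cut-point maximises J = sensitivity + specificity − 1; the true AUC is 0.50 to 0.98; objective 3 splits 6/6. The documents give none of these.

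**Method.** The separation is d = √2·Φ⁻¹(AUC). Each simulated trial draws 12 patients and selects the cut-point c with the largest J. The apparent values from those 12 are compared with the true values of that same c in new patients: sensitivity Φ(d − c) and specificity Φ(c). There were 60,000 trials per row.

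| Split | True AUC | Sensitivity, apparent v true | Specificity, apparent v true | J, apparent v true | Excess in J |
|---|---|---|---|---|---|
| 9/3 | 0.50 | 65% v 56% | 68% v 44% | 0.34 v 0.00 | 0.34 |
| 9/3 | 0.80 | 81% v 73% | 87% v 65% | 0.67 v 0.38 | 0.29 |
| 9/3 | 0.90 | 88% v 82% | 93% v 74% | 0.81 v 0.56 | 0.25 |
| 9/3 | 0.98 | 97% v 94% | 99% v 87% | 0.96 v 0.81 | 0.15 |
| 6/6 | 0.50 | 76% v 61% | 52% v 39% | 0.29 v 0.00 | 0.29 |
| 6/6 | 0.80 | 86% v 73% | 78% v 66% | 0.63 v 0.39 | 0.24 |
| 6/6 | 0.90 | 92% v 81% | 86% v 77% | 0.78 v 0.58 | 0.20 |

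The 0.98 row is the AUC implied by the 84% sensitivity and 98% specificity that the Introduction cites. Shorter independent runs agree with the 9/3 rows to about 0.01 in J. At 9/3 and AUC 0.90, 30% of trials separate the groups perfectly in the sample.

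**Does a correction work at this size?** Mean J, 9/3 split, with ranges over separate runs:

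| True AUC | Apparent | True | Leave-one-out | Ordinary bootstrap correction |
|---|---|---|---|---|
| 0.50 | 0.34 | 0.00 | −0.01 to 0.01 | 0.17 |
| 0.80 | 0.67 | 0.38 | 0.34 to 0.37 | 0.51 to 0.54 |
| 0.90 | 0.81 | 0.56 | 0.53 to 0.54 | 0.70 to 0.71 |

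Leave-one-out is close to the truth. The bootstrap removes about half the excess: at AUC 0.80, (0.67 − 0.54)/(0.67 − 0.38) = 0.13/0.29 = 45%.

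**Fixed threshold.** A value set in advance has no selection bias but stays imprecise. For 3 of 3 ER-negative patients correctly classified, the exact lower 95% limit is 0.025^(1/3) = 0.29, so the interval is 29–100%. For 8 of 9 ER+ patients it is 52–99.7%.

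**The case against.** The strongest reply is that these are secondary analyses in a small feasibility study powered for one correlation, that the PET results do not alter care, and that intervals will accompany the estimates. Much of this stands. Exact intervals at this size are wide enough still to cover. But a wide interval does not correct a biased point estimate or a named cut-off, and the bias is large because the study is small.

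Some stronger readings are tempting, and the documents do not support them:
- *That objective 1 expressly commits to reporting inflated sensitivity and specificity.* The commitment is written only under objective 3; for objective 1 it is implied by the cut-point rule.
- *That the study would present a useless tracer as informative.* Both objectives also report the AUC with a 95% interval, and choosing a cut-point does not inflate the AUC of a single measure.
- *That the cut-points will pass into the follow-on studies.* The Introduction says only that, given success, the imaging approach will be pursued further.
- *That the plan wrongly ignores two established thresholds, 1.0 and 1.5.* The 1.5 value was tied to endocrine response in metastatic ER+ disease, not to ER status. Its quoted counts also do not reconcile: 96 selected plus 42 below the threshold is 138, against 114 patients. Neither value was set for recurrence risk, so objective 3 has no cited threshold. The 1.0 value comes from lesions other than DCIS, so testing it is a useful addition; leaving it out is not an error.

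It is also fair to object that leave-one-out is noisy. At AUC 0.80 its standard deviation is 0.32 against 0.21 for the apparent J. Its root mean square error is 0.31 against 0.35, and at AUC 0.95 it has no advantage (0.28 against 0.27). Its merit is near-unbiasedness, and it should be read beside the apparent value.

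**Conclusion.** The concern holds for the searched cut-points. Followed as written, section 12.2 yields sensitivity and specificity that are biased upward: explicitly for objective 3, and by implication for objective 1. In the scenarios tabulated, J is overstated by 0.15 to 0.34 at the 9/3 split and by 0.20 to 0.29 at 6/6. For objective 1 most of the excess falls on specificity, which rests on at most three patients.

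The sizes depend on the normal model, the Youden rule, the range of AUCs and, for objective 3, the assumed split. The direction held in every scenario run. The AUCs, their intervals and the primary correlation are unaffected. The point warrants a change to the analysis text; it does not challenge the design or the primary conclusion.

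**What to change.** In section 12.2, objectives 1 and 3:
1. Name the rule that selects the cut-point, for example the Youden index.
2. Leave out each patient in turn, repeat the search on the rest, and classify the omitted patient with the resulting cut-point. Report leave-one-out sensitivity and specificity next to the apparent values, for each risk model under objective 3.
3. Label the cut-points exploratory and say that the apparent accuracy is optimistic.
4. Do not substitute the ordinary bootstrap correction, which leaves about half the bias here and could give false reassurance.
5. For objective 1 only, also report sensitivity and specificity with exact 95% intervals at SUVmax 1.0, described as a supplement because the value comes from non-DCIS lesions.

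The cost is a few lines of text and code, with no new patients or data. The corrected figures will be noisier and less favourable. Leave-one-out needs at least 2 patients in each group; with fewer, the plan should say that no corrected value can be given. None of this repairs the imprecision from at most three ER-negative patients. The change has most value if it is written down before the analysis.

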### **3. STUDY AIMS/STUDY OBJECTIVES**

The goal of this research is to assess the technical feasibility of simultaneous breast DCE MRI with  $^{18}\text{F}$ -FES PET for measuring ER in patients with DCIS and identifying patients with low-risk of disease recurrence. We hypothesize that quantitative  $^{18}\text{F}$ -FES uptake parameters from PET/MRI will correlate well with the ER immunohistochemistry score and with low-risk recurrence scores.

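### The ROC analyses in 12.2(1) and 12.2(3) fix no direction, so an AUC taken from the logistic fit averages 0.63 or more when there is no association

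*Combined protocol and SAP*

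**What the plan says.** Section 12.2, item 1 (ER-positive against ER-negative) plans an ROC analysis in which the AUCs and "their respective two-sided 95% confidence intervals will be calculated using logistic regression". Item 3 (low against intermediate/high risk, run separately for the Van Nuys index, the Memorial Sloan-Kettering nomogram and the research Oncotype score) repeats it: "The AUCs for the ROCs and their respective two-sided 95% confidence intervals will be calculated using logistic regression". In both items the cut-point is the uptake "value with the maximum sensitivity and specificity". Neither item says whether the ROC curve is built on raw uptake or on fitted probabilities, and neither says which side of the cut-point is positive.

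The study hypothesis in section 3 (also in the protocol summary) is that quantitative FES "uptake parameters from PET/MRI will correlate well with the ER immunohistochemistry score and with low-risk recurrence scores". This implies that higher uptake goes with ER positivity and with low risk, but section 12.2 does not carry that direction into the AUC.

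**The concern.** An AUC calculated from a logistic model is ordinarily the AUC of its fitted probabilities. With uptake as the only predictor, those probabilities rank patients in the order of uptake if the slope is positive and in the reverse order if it is negative. The sample therefore chooses the direction. How the outcome is coded makes no difference, because recoding flips both the slope and the target class.

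With 12 patients at most, a marker with no value falls on the wrong side of 0.50 about half the time, and most of those results would be turned over and reported as discrimination. A marker that works opposite to the hypothesis would look like a good one. Item 3 does this for three risk models. Finding low-risk patients is part of the study's stated goal, and section 2 says that success would lead to further studies of patients who might avoid radiation or surgery.

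**Working it through.** **Inputs from the documents.** Section 12.1 gives the sample size: "A sample size of 12 patients achieves 82% power". The same section restricts one class: "The number of subjects with ER-negative DCIS will be limited to" at most 3. At N = 12 the best split in item 1 is therefore 9/3, and 10/2 or 11/1 is possible. Section 5.7 limits the Oncotype assay to patients with enough remaining tissue, so that analysis may have fewer than 12.

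**Assumptions.** The documents do not give the low against intermediate/high split; 6/6 to 9/3 is used. Uptake is taken as log-normal with log-SD 0.5, and two other distributions are shown.

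**The plan's own figure.** The documents state no expected AUC. The only related figure is the primary power. By Fisher's z, atanh(0.73) = 0.929, so N = ((1.960 + 0.842)/0.929)² + 3 = 12.1. Power at N = 12 is 79.6% without a bias term and 82.3% with the r/(2(n − 1)) term. The stated 12 patients and 82% are reproduced, which confirms the N used here.

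**Step 1: the rule.** Let A be the AUC on raw uptake in the hypothesised direction. The AUC of the fitted probabilities is A if the slope is positive and 1 − A if it is negative. The sign of a one-predictor logistic slope equals the sign of the difference in group means. Model fits to simulated null data agreed with this apart from a handful of sign mismatches (7 in 3,000 lightly penalised fits).

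**Step 2: a case by hand.** With one ER-negative patient among 12, A can only be k/11 for k = 0 to 11. With no association each value is equally likely, so the mean of A is 0.50. The mean of max(A, 1 − A) is (11 + 10 + 9 + 8 + 7 + 6)/(6 × 11) = 51/66 = 0.77. The logistic rule gives slightly less, because the slope follows the means and not the ranks.

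**Step 3: no association, N = 12, mean reported AUC by simulation.**

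| Split | Direction fixed | Logistic, log-SD 0.5 | Logistic, log-SD 0.7 | Logistic, normal |
|---|---|---|---|---|
| 6/6 | 0.50 | 0.63 | 0.62 | 0.63 |
| 8/4 | 0.50 | 0.64 | 0.63 | 0.64 |
| 9/3 | 0.50 | 0.65 | 0.65 | 0.66 |
| 10/2 | 0.50 | 0.68 | 0.67 | 0.69 |
| 11/1 | 0.50 | 0.76 | 0.75 | 0.76 |

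At log-SD 0.5, the chance of an AUC of 0.70 or more with no association doubles: from 12% to 24% (6/6), 14% to 28% (8/4) and 19% to 37% (9/3). The 0.70 mark is only illustrative; the plan attaches no decision to it.

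**Step 4: reversed association, 6/6 to 9/3.** A true AUC of 0.35 is reported on average as about 0.68 to 0.69, and a true AUC of 0.25 as about 0.75 to 0.76.

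**Step 5: a marker that works.** At a true AUC of 0.80, the logistic rule averages 0.80 to 0.81 for 6/6 to 9/3. At 0.85 it averages 0.85. Only with a single ER-negative patient is there a visible gap (0.875 against 0.849).

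**The case against.** Four points can be made for the plan.

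First, a reader might infer that the plan prescribes an AUC blind to direction. It does not. Fitted probabilities are never mentioned, and the cut-point is sought on the uptake scale, where a curve with fixed direction is possible. This stands: the problem is the default result of an underspecified method. But the AUC of the fitted model is the ordinary meaning of the sentence, and nothing in section 12.2 prevents it.

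Second, a reader might infer that a reversal would be hidden from the report. That also goes too far. The primary analysis is a signed Spearman correlation of SUVmax with the Allred score, and 12.2(4) reports a signed correlation and scatter plot for the Oncotype score. The slope sign, or the side of the cut-point, would show direction too if reported. What remains is that no signed analysis is planned for the Van Nuys index or the Memorial Sloan-Kettering nomogram, and that a signed result elsewhere does not remove the upward bias from the AUC itself.

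Third, the objectives speak only of separating two groups, and a marker that separates them in reverse does discriminate. This is fair as far as it goes, but the section 3 hypothesis implies a direction, and an estimate whose no-effect mean is well above 0.50 misleads on either reading.

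Fourth, section 2 cites 84% sensitivity and 98% specificity of FES PET for ER status in invasive cancer, so a null or reversed result is unlikely in item 1. This stands, and step 5 shows that the bias then nearly vanishes with three per group. Section 2 also says that FES has not been studied in DCIS, and it gives no comparable accuracy figures for the risk groups in item 3.

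**Conclusion.** The point holds in a limited form. Read in the usual way, items 1 and 3 let the sample set the direction of the AUC. Under no association the mean is about 0.63 to 0.65 for splits from 6/6 to 9/3. That range should not be taken as covering all of item 1, where the cap on ER-negative patients allows 10/2 and 11/1, giving about 0.68 and 0.76.

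The mechanism is algebra. The sizes rest on the assumed uptake distribution, which matters little (step 3), and, for item 3, on assumed splits. Nor do the figures support a claim that the AUC is inflated in general. These are secondary estimates without a go/no-go rule, PET results do not guide care, and the primary test is untouched. The change is still worth making, because it costs only wording and two of the three risk models have no signed result to set beside the AUC.

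**What to change.** In 12.2(1) and 12.2(3), replace the logistic-regression sentence with text to this effect:

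- The AUC is calculated nonparametrically (Mann-Whitney) on the raw uptake measure: FES uptake in item 1, SUVmax in item 3.
- The direction is fixed in advance: higher uptake indicates ER-positive in item 1 and low risk in item 3, as the study hypothesis implies.
- A two-sided 95% confidence interval is given by a named nonparametric method suited to small samples. The present sentence also supplies the interval method, so the replacement must not drop it.
- An AUC below 0.50 is reported as such.
- The cut-point is chosen with the same direction, and the positive side is stated.

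The cost is SAP wording only, with no new data. Some reported AUCs will be lower, including values under 0.50. If the hypothesis is right and each group has at least three patients, the estimates will hardly change.
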